## 1. Background and rationale

Emerging data suggest minority individuals are at an increased risk of acquiring SARS-CoV-2 infection and experience worse clinical outcomes from COVID-19 compared to White individuals. Geographic locations reporting data by race/ethnicity indicate that African American individuals and Latino individuals bear a disproportionate burden of COVID-19-related outcomes. Blacks are experiencing a 2.7 times higher COVID-19 death rate as compared to whites, whereas Latinx are experiencing a 2.5 times higher rate. In California, Asian Americans have been disproportionately affected by the COVID-19 pandemic accounting for at least 7% of COVID-19 cases and 15% of COVID-19 related deaths with a case fatality rate of 8.4% in California far exceeding that of the overall population (2.6%).

The reasons for COVID-19 disparities among underserved minorities are complex and intertwined including a disproportionate burden of underlying comorbidities, being uninsured or having access issues, and holding public facing occupations with greater exposure risk. It has been noted how minority status and language, household composition and transportation, are the greatest current predictors of COVID-19 case counts in the U.S..

At this time, COVID-19 testing is predominantly comprised of diagnostic testing, where suspected positive cases, i.e. symptomatic individuals, are tested, with the primary aim of limiting further person-to-person transmission. There is currently limited data on COVID-19 screening among asymptomatic individuals, especially among more vulnerable populations. Prior coronavirus outbreaks have shown asymptomatic spreaders to comprise a high proportion of infected individuals and identifying these individuals as important for containing further viral transmission. Contact tracing and testing of individuals of high-risk of COVID-19 exposure is the current public health focus for bending the curve.

Urban schools serving underserved communities (e.g., majority underrepresented minority students, > 50% qualifying for free/reduced price meals, those with high percentage of English language learners) lack the personnel and logistical support to implement robust COVID-19 screening programs as part of their COVID prevention plans, even though they serve communities with some of the highest COVID infection and lowest vaccination rates.

Rapid antigen testing (results in <15 minutes) offers substantial advantages in the school setting, quickly identifying (and isolating) positive cases and significantly lowering cost relative to PCR testing. However, it requires significant logistical planning and staffing. Providing unvaccinated students and school staff with free at-home over the counter (OTC) antigen test kits would dramatically reduce the burdens of implementing school testing screening programs for disadvantaged school settings.

In particular, equitable access to simple, convenient, regular at-home COVID screening testing for unvaccinated middle school students, staff, and their families in disadvantaged schools can have substantial impact on reducing household, school, and community transmission. At-home testing timed right also reduces the economic consequences from school exposure quarantines. At-home antigen testing also promises broader testing access (in line with Presidential COVID response plan priorities) and, in the school setting, can reduce within-school transmission and absenteeism from post-exposure group quarantine.

## 2. Specific objectives

**Aim 1.** We will determine if providing free at-home COVID-19 rapid antigen testing kits produces equivalent participation in and adherence to school screening testing as on-site school testing. In a non-inferiority trial, we will evaluate if, with appropriate educational materials and support (e.g., videos, a helpline, all in multiple languages, outreach,

reminders, follow-up support, etc.) providing at-home testing kits produces roughly equivalent weekly participation and adherence rates in the school screening testing program as on-site antigen testing.

**Aim 2.** We will evaluate if a family-based model of making testing available to family members enhances student and school staff participation.

**Aim 3.** [not part of clinical trial] We will also study implementation of the program to inform our scale-up to additional schools and identify resources needed to ensure ongoing high participation rates.

**Aim 4.** [not part of clinical trial] We will assess acceptability and feasibility of at-home COVID-19 testing.

### **3. Methodology**

#### **3.1 Setting and population.**

##### **Research setting.**

This study will take place with Sweetwater Union High School District (SUHSD), a public school district in South San Diego County along the US-Mexico border, that serves 90% racial and ethnic minority students and a high proportion of socioeconomically disadvantaged students (66% of middle school students eligible for free/reduced meals). It is the second largest school district in San Diego County and the largest secondary school district in CA (>39,000 students). It includes middle schools, a junior high, and high schools. The proposed project will focus on ten middle schools and one junior high (10,160 students, 893 staff). The district serves one of the largest proportions of racial and ethnic minority students in the county and CA; 72.4% of students are Latino/a and 8.5% Filipino (vs. 54.9% Latino/a and 3.7% Filipino in San Diego County schools). Over a fifth (21.2%) of students are English-language learners and half speak a language other than English at home. The district's academic year begins on July 21, 2021.

**Study population.** There are 10 middle schools and 1 junior high school eligible for inclusion, all in the Sweetwater Union High School District. Three will be selected to participate in the noninferiority trial. Schools will be excluded from possible selection if they have a lower proportion of students from households receiving Supplemental Nutrition Assistance Program benefits, a lower proportion of underrepresented minority students compared with other schools, have ongoing school-wide testing programs with a commercial provider, cannot be matched to other schools by population size, or are geographically close to another school.

Study participants will be students or staff at the selected SUSHD schools.

**Inclusion criteria:** SUHSD school staff member or student at a school selected for inclusion in the trial. Able to speak English or Spanish.

**Exclusion criteria:** Not a SUHSD student or staff member at a school selected for inclusion in the trial. Not able to speak English or Spanish.

#### **3.2 Study design and procedures**

##### **Recruitment, eligibility screening, and informed consent.**

Recruitment into the research study will be multi-modal. We will leverage SUHSD communication channels to reach district parents and inform them about the study. This will include email, SMS, presentations at events, and Community Health Worker-staffed tables at drop-off and pick-up times at each of the three schools. All of the aforementioned communications will be informational in nature. The "call to action" will be for parents and

students to visit the study website to review study eligibility and informed consent documents. After confirming eligibility, informed consent will take place through Qualtrics, with appropriate affirmations throughout the document to ensure understanding and a field to record signature. Study participants will be emailed a copy of the consent forms including the study details, benefits and risks, and information they may opt-out of the study at any time without risk of repercussions or loss of benefits provided outside of this study. In addition, a phone number and email address to reach SDSU study staff will be available for individuals with further questions. The study participant will be informed over the phone/email if they contact us that there are no repercussions for refusing to consent.

Consented participants will complete a 30-minute questionnaire via Qualtrics or verbally or on their own phone if registering on site.

### **Research design**

#### **Aim 1. At-home rapid antigen COVID-19 testing vs. on-site rapid antigen testing.**

Pragmatic non-inferiority trial, randomizing middle schools to either the on-site or the at-home COVID testing model. Trial duration about 5 months weeks. We will compare participation rates (percentage of the school population participating in testing) and adherence to the testing schedule (percentage of scheduled tests completed).

#### **Aim 2. Family-based model to increase student and staff participation in testing**

Quasi-experimental trial pre-post control group design. To establish a baseline (pre-test), all three schools will implement the respective testing program without the family-based model for 4 weeks. At the end of the 4 weeks the two schools in Aim 1 will implement the family-based model promoting the availability of testing for unvaccinated family members whereas the control school will not. We will track participation rates (overall and testing schedule adherence) in the three schools for 12-15 weeks post implementation of opening up testing to family members.

### **Study variables**

#### **Primary outcomes:**

- Aim 1. At-home testing vs. on-site rapid antigen testing (testing rate)
  - Participation rate: weekly percentage of students and staff (school population) who participate in testing
  - Adherence to testing schedule: percentage of scheduled weekly tests completed once a participant enrolls in the trial
- Aim 2. Family -based model to increase student and staff participation in testing
  - Participation rate over time: percentage of students and staff who participate in testing
  - Adherence to testing schedule: percentage of scheduled tests completed

#### **Other variables assessed:**

- Sociodemographics
- Housing characteristics, household employment
- Health insurance and health care access
- Health status and risk factors for severe COVID
- Prior COVID testing and beliefs about testing
- Other risk factors for COVID (smoking, vaping, alcohol use - brief)
- Disability/Functional status
- Pandemic Impacts: Economic, Housing, Food Insecurity
- COVID vaccine receipt and perceptions.
- COVID prevention, testing experience, and challenges.
- COVID symptoms and exposure

- [not part of clinical trial] Implementation outcomes and CFIR^12 constructs
  - Acceptability: Perception that the testing approach is agreeable or satisfactory
    - recipients of testing: client satisfaction scale,
    - testing program staff: 4 item acceptability scale
    - Meeting notes from staff.
    - Stakeholders: listening sessions with parents/guardians, meeting notes from stakeholder meetings
  - Appropriateness: Perceived fit, relevance, or compatibility of the COVID testing program for a given individual or staff and/or the perceived fit of the approach to address problems with alternative COVID testing approaches and aspects of safe return to school programs
    - recipients of testing: 4 item appropriateness scale collected after testing.
    - staff: 4 item appropriateness scale completed after training and 1 month into implementation.
    - Meeting notes from staff meetings
    - Stakeholders: listening sessions with parents/guardians, meeting notes from stakeholder meetings
  - Feasibility: Extent to which the testing approach can be successfully implemented
    - stakeholders: listening sessions with parents/guardians; meeting notes from stakeholder meetings
    - testing program staff: 4 item feasibility scale & staff notes
  - Fidelity: Testing program implemented as intended
    - Review of study records.
    - Throughout implementation
- Assessment of modifiable factors which can enhance implementation efficacy during scale-up
  - Intervention Characteristics: Relative advantage, adaptability, complexity/perceived difficulty, design quality & packaging
  - Outer Setting: Student/parent/staff needs & resources, policies and incentives, peer pressure
  - Inner Setting: Structural characteristics, implementation climate, tension for change, relative priority, leadership engagement, available resources, learning climate, networks and communication
  - Characteristics of individuals: Knowledge and beliefs about testing approach, self-efficacy
  - Process: Executing, reflecting and evaluating, external change agents, champions, key stakeholders

### 3.3 Data collection

**Aims 1 and 2.** Baseline Questionnaire: Upon enrollment into the study, we will collect RADx-UP Tier 1 Common Data Elements (including demographics, household characteristics, pandemic effects on household employment, pandemic effects on access to health care, risk factors for severe COVID, COVID vaccination status, intentions, hesitancy, prior COVID testing and beliefs about testing, other COVID risk factors, and contact information.

Each time they test, participants (parent/guardians for participants under age 11) will self-report COVID symptoms to determine if post-antigen PCR confirmatory testing is needed (see “symptom and exposure report at the time of testing” document). We will observe the number of COVID cases at participating schools by grade and among staff each month from cases diagnosed outside our testing program.

Adult participants (school staff) aged 18 and above including any students aged 18 and above will complete the questionnaires themselves. Participants aged 11-17 will answer the majority of the questions in the questionnaires themselves with some questions about the household and background health history being completed by a parent/guardian who is asked to report about the child. For participants below age 11, a parent or guardian will complete the questionnaires reporting about the child.

**COVID-19 testing approach and frequency of testing.** Weekly screening testing with rapid antigen tests will be available for students and staff. We will follow CDC antigen testing algorithms and any changes (current: confirmatory PCR in asymptomatic antigen+ and symptomatic antigen- cases). We will use the Quidel QuickVue COVID-19 antigen tests, available as both a point-of-care CLIA waived test and an at-home OTC test with results in 10 minutes. For the at-home OTC test an adult collects the sample of children <14 years. In the current EUA, the OTC test is used as a serial test to improve sensitivity, with a first test followed 24-36 hours later by a second test. However, a mobile app to interpret the test results with a smartphone or tablet camera is expected to be released soon and per the 03/31/21 EUA will change the testing procedure from serial testing to a single test. Although we expect the updated EUA to be issued prior to our project start date, we will use serial testing if needed to begin.

**Monitoring of safety and mitigation measures.** Although SUHSD’s 2021-22 COVID-19 safety/mitigation plan has not yet been finalized, we anticipate indoor mask requirements, HVAC system ionizers, engineering controls (e.g., ventilation modification), cleaning/disinfection practices, and physical distancing with possible daily temperature checks. We will document plan details and modifications and account for them in our testing program impact analyses.

**COVID-19 onsite results, case reporting, and follow-up support.** All test results in onsite antigen testing are provided in individual privacy tents to maintain confidentiality and to provide a place for students with positive results to wait until a parent or guardian arrives to pick them up. School-affiliated antigen+ cases in onsite testing are reported immediately to the school nurse and District COVID-19 response team lead, and to the County of San Diego (CoSD) Epidemiology team at the end of the day, which satisfies County and State reporting requirements. Site-related close contacts are evaluated by the District COVID-19 team during a support call with the parent/guardian, which also functions to provide isolation instructions, procedures to safely return to campus, and referrals for resources (food, medical, social support, academic support). Support calls are repeated partway through the isolation period. Additional steps such as close contact quarantine are taken as necessary. Confirmatory PCR results are also communicated by the District COVID-19 response team.

### **3.4 Statistical Analysis Plan**

**Aims 1 and 2.** All analyses will follow the intention-to-treat principle.

This study is designed to determine if at-home COVID-19 testing is noninferior to onsite testing for participation rates and adherence to weekly testing. We selected a noninferiority margin of 6%, because of the significant advantages of an at home COVID-19 testing program in implementation resources and reducing at-school exposures.

The necessary sample size was calculated as 324 per arm (type I error rate 0.05, power 80%) for both outcomes.

We plan to use generalized estimating equations models with a logit link and will evaluate correlation structure selecting correlation structure based on model fit. We anticipate a first-order autoregressive correlation structure to account for the time dependence within each participant. Models including covariates, such as participant type (student, staff), race and ethnicity, primary language spoken at home, gender identity, COVID-19-vaccination status, and prior COVID-19 testing among interaction terms, will be evaluated.

The first outcome, participation rate in testing over time, utilizes the school population sample of both enrolled and non-enrolled participants using school demographic data. Therefore, models for this outcome will only have basic demographic covariates of participant type, race and ethnicity, and gender identity since these demographics were available by school. Estimated marginal means (model predicted probabilities) and standard errors for the outcomes for each study arm, controlling for covariates, will be generated for testing the noninferiority hypotheses. Exploratory subgroup analyses will be conducted for covariates that showed differences between the arms. One-sided noninferiority tests for participation rates and adherence proportions between the 2 study arms will be assessed. One-sided 95% confidence intervals for all models will be constructed.

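### Does the lack of a stated rule linking the two Aim 1 noninferiority tests (participation, adherence) undermine the error rate or the 80% power?

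*Combined protocol and SAP*

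**What the plan says.** The primary outcomes list under Study variables gives two measures for Aim 1. Participation is the "weekly percentage of students and staff (school population) who participate in testing". Adherence is the "percentage of scheduled weekly tests completed once a participant enrolls in the trial".

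Section 3.4 states a single objective, to determine whether at-home testing is "noninferior to onsite testing for participation rates and adherence to weekly testing". It sets one margin of 6% and one sample size: "The necessary sample size was calculated as 324 per arm (type I error rate 0.05, power 80%) for both outcomes". On testing it says: "One-sided noninferiority tests for participation rates and adherence proportions between the 2 study arms will be assessed". It adds: "One-sided 95% confidence intervals for all models will be constructed". The participation analysis "utilizes the school population sample of both enrolled and non-enrolled participants using school demographic data".

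No section gives an order of testing, a multiplicity procedure, a joint power, or a correlation between the two outcomes.

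**The concern.** Two primary tests without a success rule normally raise one of two problems.

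- **Both must pass.** The error rate is safe, but the power to pass both cannot exceed the smaller of the two powers. If each is exactly 80%, the power for the combined claim is lower.
- **Either suffices.** Power is at least 80%, but two unadjusted tests at 0.05 can give a false claim more than 5% of the time.

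The outcomes also cover different people. Participation counts the whole school; adherence counts only those who enrol. At-home testing could therefore look noninferior on adherence while fewer people took part. Without a rule, someone could choose after seeing the data which result carries the claim.

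**Working it through.** **Inputs.** From section 3.4: 324 per arm, error rate 0.05 (one-sided, matching the one-sided 95% intervals), power 80%, margin 6%, taken here as 6 percentage points. From section 3.1: 10,160 students and 893 staff in 11 schools. Assumed, because the documents give no figure: no true difference, the correlation r between the two test statistics, and one school per arm. The last is suggested by the Aim 2 design, which refers to two schools in Aim 1. School clustering and repeated weekly measures are ignored throughout.

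**1. The plan's own figure.** n per arm = 2p(1 − p)(1.645 + 0.842)² / 0.06². This gives 323 at a common rate p of 10.5% or 89.5%, 310 at 90%, 550 at 80% and 859 at 50%. The plan states no rate, so 324 can be back-solved (p near 10.5% or 89.5%) but not confirmed.

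**2. The figures that cause alarm.** Let B(a, b; r) be the probability that two standard normals with correlation r fall below their a and b quantiles. For r = 0, 0.5 and 0.9:

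| Quantity | r = 0 | r = 0.5 | r = 0.9 |
|---|---|---|---|
| Power to pass both, B(0.80, 0.80; r) | 64% | 69% | 75% |
| Power if either suffices, 1.60 − B(0.80, 0.80; r) | 96% | 91% | 85% |
| Error if either suffices, 0.10 − B(0.05, 0.05; r) | 9.75% | 8.8% | 6.8% |

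To restore 80% joint power at r = 0, each test would need 89.4% power: 324 × 1.356 = 440 per arm. The arithmetic is right, but it gives participation only 80% power, as if it were analysed on 324 people per arm.

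**3. Participation on the sample that the plan specifies.** The mean school population is (10,160 + 893) / 11 = 1,005. If 324 per arm gives 80% power, then with the rate and true difference unchanged, n per arm gives Φ(√(n/324) × 2.487 − 1.645).

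- n = 1,005: √(1,005/324) = 1.761, so Φ(4.379 − 1.645) = Φ(2.734) = 99.7%.
- n = 500: √(500/324) = 1.242, so Φ(3.089 − 1.645) = Φ(1.444) = 92.6%.

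With adherence at 80%, joint power at r = 0 is 0.997 × 0.80 = 79.7% for the average roster and 0.926 × 0.80 = 74% for a roster of 500. As r rises to 0.9, both approach 80%.

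**4. If participation is not near the implied rate.** With 1,005 per arm, power = Φ(0.06 / √(2p(1 − p)/1,005) − 1.645). Joint power at r = 0, with adherence at 80%:

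| Participation rate | Power for participation | Joint power |
|---|---|---|
| 10% | 99.8% | 79.8% |
| 20% | 95.7% | 76.6% |
| 30% | 90.1% | 72.1% |
| 40% | 86.4% | 69.2% |
| 50% | 85.2% | 68.2% |

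**5. The possible claim structures side by side.** Both must pass: the error rate of the claim is at most 0.05, and only power is in question. Separate conclusions: each statement has error 0.05, and a split result reads as adherence noninferior, participation not shown. Either suffices: error can reach 9.75%, but nothing in the plan words the objective this way.

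**The case for a change.** The strongest case for a change is that the rule is missing and would cost one sentence. A split result is foreseeable. Schools are randomised and individuals consent afterwards, so a smaller, keener group could enrol in one arm and hold adherence up while participation falls. Settling the rule beforehand removes any later choice. A 50% participation rate would also leave a visible power shortfall even on the full roster.

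Much of this stands. The documents state no rule and do not say whether 80% is joint or per outcome. A joint reading cannot be excluded by arithmetic, because 324 would then imply rates near 7.5% or 92.5%, which are equally unstated. A sentence in 3.4 would do no harm.

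It does not show that anything in the plan is wrong. A both-must-pass sentence would only write down what the objective already says. Testing participation first would impose a ranking that the plan does not make. The plan already pairs adherence with a whole-school outcome that can reveal an enrolment loss, and both are tested, so a split result cannot hide it. Selection after enrolment, its fit with the commitment that "All analyses will follow the intention-to-treat principle", and school clustering are separate questions. A rule linking the two tests would resolve none of them.

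**Conclusion.** No change is needed. This is a gap that analysts would fill sensibly. On the plainer reading, noninferiority on both outcomes with 80% power each, the one-sided 0.05 is preserved and the power line is coherent. On the separate-conclusions reading, each result is sound at its own level. The inflated error of up to 9.75% arises only under an either-suffices rule, which the plan does not state.

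The power at stake is uncertain but much smaller than the 64% and 440 per arm suggest. With adherence at 80% and the implied rates unchanged, joint power is about 74% to 80% for rosters of 500 to 1,005. On the average roster with independent tests, it is about 68% to 80% for participation rates of 50% down to 10%. These ranges rest on assumed rates, no true difference and one school per arm, and ignore clustering. They give the order of magnitude of the joint-power question, not the trial's actual power.

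### The 80% power stated for 324 per arm holds only if schools do not differ, because schools are randomised with one, or at most two, per arm

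*Combined protocol and SAP*

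**What the plan says.** Section 3.4 states: "The necessary sample size was calculated as 324 per arm (type I error rate 0.05, power 80%) for both outcomes". It sets the margin ("We selected a noninferiority margin of 6" per cent) and the one-sided level ("One-sided 95% confidence intervals for all models will be constructed"). It gives no expected rate, true difference, intraclass correlation, design effect or number of schools.

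The Aim 1 design in section 3.2 is a "Pragmatic non-inferiority trial, randomizing middle schools to either the on-site or the at-home COVID testing model". On the number of schools, section 3.1 says "Three will be selected to participate in the noninferiority trial", which allows two against one. The Aim 2 text in section 3.2 says "At the end of the 4 weeks the two schools in Aim 1 will implement the family-based model" and sets a control school apart from them, which implies one against one in Aim 1.

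The only dependence named for the GEE models is within person: "We anticipate a first-order autoregressive correlation structure to account for the time dependence within each participant". The participation outcome "utilizes the school population sample of both enrolled and non-enrolled participants using school demographic data", whereas section 3.2 defines adherence among people who have enrolled.

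**The concern.** A sample size given as people per arm, with an alpha and a power and nothing about clusters, has the form of a calculation for individually randomised people. Here whole schools are assigned. Any true difference between schools in uptake or adherence goes straight into the arm comparison, and it does not shrink as more people enrol within a school. With one school per arm, school and arm cannot be separated at all.

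Two misreadings follow from an unqualified 80%. A failure to show noninferiority would be read as coming from an adequately powered trial, and reaching 324 would be taken as meeting a power target. In the other direction, the same unmodelled variation makes a participant-level test too ready to declare noninferiority, so a positive result would carry more than the stated 5% error.

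**Working it through.** **Inputs.** From section 3.4: 324 per arm, power 80%, margin 6% (taken as 6 percentage points, since the scale is not stated) and one-sided alpha 0.05. From section 3.1: 11 eligible schools with 10,160 students and 893 staff. Assumed, because the documents give no value: true difference 0, and between-school SD τ of 1, 2, 3 or 5 points.

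**1. Can 324 be reproduced?** The individual-level formula with equal true rates is n = 2p(1−p)[(z₀.₉₅ + z₀.₈₀)/0.06]², with z₀.₉₅ + z₀.₈₀ = 1.645 + 0.842 = 2.4865.

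- Setting n = 324 gives p(1−p) = 0.0943, so p is about 10.5% or 89.5%.
- Other rates give 550 (20% or 80%), 722 (30% or 70%) and 859 (50%).
- If 324 already contained a design effect, the rate would have to be more extreme. At ICC 0.01 the design effect is 1 + 323 × 0.01 = 4.23, the effective n is 77, and the rate is about 2.3% or 97.7%. At ICC 0.001 the effective n is 245, and the rate is about 7.7% or 92.3%.

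So 324 is compatible with no cluster inflation at a plausible rate. Since no rate is stated, this cannot be confirmed. With only 11 eligible schools, 324 must count people.

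**2. Standard error implied by the stated power.** 80% power for a 6-point margin needs SE = 6/2.4865 = 2.413 points. The steps below take 324 per arm as delivering exactly this SE when there is no clustering.

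**3. Adding schools.** The true SE becomes √(2.413² + cτ²), with c = 1 + 1 = 2 for one against one and c = 1/2 + 1 = 1.5 for two against one.

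- *Planned participant-level test* (the test uses 2.413, while the estimate varies with the true SE): power = Φ[(6 − 1.645 × 2.413)/true SE] = Φ[2.031/true SE]; type I error = 1 − Φ[3.969/true SE].
- *Between-school SD known and allowed for*: power = Φ[6/true SE − 1.645].

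One school against one, 324 per arm:

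| τ (points) | True SE | Power, participant-level SE | Type I error, participant-level SE | Power, τ known |
|---|---|---|---|---|
| 0 | 2.41 | 80% | 5% | 80% |
| 1 | 2.80 | 77% | 8% | 69% |
| 2 | 3.72 | 71% | 14% | 49% |
| 3 | 4.88 | 66% | 21% | 34% |
| 5 | 7.47 | 61% | 30% | 20% |

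Two against one, at τ = 2, 3 and 5: 72, 68 and 62% with participant-level SEs; 54, 39 and 23% with τ known.

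**4. Limits at any number of participants.** With τ known, 80% needs √c·τ ≤ 2.413, so τ ≤ 1.71 points (one against one) or 1.97 (two against one). With participant-level SEs and unlimited people, power tends to Φ[6/(√c·τ)], so the limits are 6/(0.842 × √2) = 5.04 and 6/(0.842 × √1.5) = 5.82 points.

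**5. Participation.** Its denominator is the school population, on average (10,160 + 893)/11 = about 1,005 per school. Scaling, SE = 2.413 × √(324/1,005) = 1.370 points. Participant-level power at τ = 1, 2, 3 and 5 (one against one) is then about 97, 88, 80 and 70%. The same formula for type I error, 1 − Φ[1.645 × 1.370/true SE], gives about 13, 24, 31 and 38%.

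**The case against.** The strongest objection is that the planned analysis has no school term, so the severe figures (69, 49, 34 and 20%, and the 1.7-point ceiling) describe a test that the plan does not propose. With one school per arm that test could not be run, because it needs a between-school SD that these data cannot supply. This stands. A reader might infer that above 1.7 points no enrolment gives 80% power in this trial. The documents support that only for a test with known SD; under the planned participant-level test the ceilings are 5.04 and 5.82 points. The higher power of that test comes with an inflated type I error, so it is no defence of the stated design values.

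Second, a reader might apply the shortfall at 324 to both outcomes, since the plan gives 324 for both. That does not hold: participation uses the whole school, and its participant-level power stays at or above about 80% up to an SD of 3 points. Its type I error is worse, not better.

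Third, a reader might conclude that 324 is an arithmetic error. That is not shown. No rate or ICC is stated, and a small design effect with a more extreme rate is possible.

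Fourth, section 3.1 excludes schools that cannot be matched on population size and restricts on household benefits and minority share, and section 3.4 adjusts for covariates. These may reduce between-school variation. They do not make it zero, and none is a match on testing uptake. No value in the assumed SD range is anchored in the documents.

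**Conclusion.** The point holds in limited form. The stated 80% power, and the 5% error that goes with it, belong to an individually randomised comparison with no between-school variation; the design randomises schools with one or at most two per arm. For adherence at 324 per arm with one school per arm, between-school SDs of 1 to 5 points take participant-level power from 80% down to between 77 and 61%, and one-sided type I error from 5% up to between 8 and 30%. These sizes rest on a true difference of zero, a margin in absolute points, 324 giving exactly 80% without clustering, and SDs that are assumed. That 324 contains no cluster inflation is a firm inference, not a demonstration. The known-SD powers are illustrative only. The documents do not support a claim that the trial must add schools or people; what needs correcting is the statement of what 324 delivers.

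**What to change.** In section 3.4, replace the unqualified power statement with wording such as:

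> 324 per arm is a recruitment target for the adherence outcome. It gives 80% power only under individual randomisation, that is, assuming no between-school variation. Schools are the randomised unit, with one or two per arm, so between-school variation cannot be reliably separated from the arm effect, and 80% power and 5% type I error are not guaranteed at any number of participants.

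In the same paragraph:

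- State the rates assumed in reaching 324.
- Treat participation separately, with the school population as its denominator.
- If illustrative powers are shown, label the between-school SD as assumed and give both the participant-level and the known-SD figures, with the type I error beside the former.
- Reconcile sections 3.1 and 3.2 on whether Aim 1 has two schools or three.

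The cost is one SAP paragraph and a less favourable power statement. Recruitment, schools and procedures do not change.
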